4. Patients must be eligible to undergo kidney transplantation from a living or deceased donor, as per institutional standards.
5. Female patients of non-childbearing potential must be either surgically sterile (hysterectomy, bilateral tubal ligation, salpingectomy, and/or bilateral oophorectomy at least 26 weeks before Screening) or postmenopausal, defined as spontaneous amenorrhea for at least 2 years, with follicle-stimulating hormone in the postmenopausal range at Screening, based on the laboratory's reference range.
6. Female patients of childbearing potential (ie, not postmenopausal or surgically sterilized) must have a negative urine or serum pregnancy test result at Screening. Participating female patients of childbearing potential must agree to use 1 of the following throughout the duration of the study and for 90 days following the last study drug administration:
 - One highly effective method of contraception and an acceptable barrier method (condom used by male partner plus spermicide).
 - Two highly effective methods of contraception.

Investigators will select the appropriate methods of contraception in accordance with local regulatory requirements. Highly effective methods of contraception that result in a low failure rate (ie, <1% per year) when used consistently and correctly include the following:

- Combined (estrogen and progestogen containing) hormonal contraception associated with inhibition of ovulation (oral, intravaginal, or transdermal), progestogen-only hormonal contraception associated with inhibition of ovulation (oral, injectable, or implantable), intrauterine device, or intrauterine hormone-releasing system for at least 12 weeks before Screening.
- Bilateral tubal occlusion or vasectomized partner at least 26 weeks before Screening.

Note: A vasectomized partner is a highly effective method of contraception, provided that the male partner is the sole sexual partner of the study patient who is a female of childbearing potential and that the vasectomized partner has received medical assessment of surgical success.

- Sexual abstinence.

Note: True abstinence, when in line with the preferred and usual lifestyle of the patient, is considered a highly effective method only if defined as refraining from heterosexual intercourse during the entire period of risk associated with the study drug treatment.

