NPC-21 is a human monoclonal immunoglobulin G1 (IgG1) lambda against the AD-1 on hCMV gB. Antigenic domain 1, the dominant antigen of the hCMV envelope, is reported to exhibit little sequence variation in clinical isolates of hCMV.¹³ A cell clone that produces NPC-21 was selected from B-lymphocytes isolated from peripheral blood of a healthy individual with a history of CMV infection. NPC-21 is produced by recombinant DNA technology in Chinese hamster ovary cells. NPC-21 has been demonstrated *in vitro* to inhibit infection of a cultivated CMV strain in the pharmacology study using ARPE-19 cell (epidermal cell line).

NPC-21 is a non-immunomodulatory human monoclonal antibody with a relatively safe toxicological profile, causing no deaths and producing only mild reversible changes in hematological parameters (ie, decreased erythrocyte count, hematocrit value, and hemoglobin concentration) following repeated dosing in monkeys. Additionally, no cross reactivity was seen in a study of cross reactivity in human and monkey tissue. Although these changes occurred at a dose with sufficient safety margins and after repeated doses, the hematology parameters will be carefully monitored in clinical studies.

A first-in-human study was conducted in 40 healthy Japanese and Caucasian male volunteers in which NPC-21 or placebo was infused over a duration of 60 minutes. This single ascending dose study confirmed tolerability of NPC-21 up to 20 mg/kg, with no serious adverse events (SAEs), ADRs, or withdrawals due to adverse events. Anti-NPC-21 antibodies were detected in some subjects, although all were found to be preexisting conditions.

Taken together, nonclinical data and clinical data available to date support further clinical investigation of NPC-21 in the prevention of CMV disease.

In March 2020, the Coronavirus Disease 2019 (COVID-19), caused by infection with severe acute respiratory syndrome coronavirus 2, was characterized as a pandemic by the World Health Organization (WHO). The COVID-19 pandemic impacted clinical studies worldwide due to quarantines, site closures, travel limitations, diversion of resources, and/or general interruptions in study-related procedures.

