4.3 Withdrawal Criteria

Patients may be discontinued from study drug for any of the following reasons:

- The patient no longer meets all inclusion criteria or meets any exclusion criteria and is found to be ineligible for participation through procedures (eg, medical examinations) performed after Randomization.
- Occurrence of any medical condition or circumstance that exposes the patient to substantial risk and/or does not allow the patient to adhere to the requirements of the protocol.

- Any SAE, clinically significant adverse event, severe laboratory abnormality, intercurrent illness, or other medical condition that indicates to the Investigator that continued participation is not in the best interest of the patient.
- Pregnancy.
- Requirement of the following therapy:
 - CMV hyperimmune globulin (eg, CytoGam®).
 - IVIg.
 - Plasmapheresis.
- Patient failure to comply with protocol requirements or study-related procedures and the Investigator considers it inappropriate to administer the study drug.
- Initiation of Rescue Phase.

Patients who discontinue study drug for any reason should be followed per the study schedule of events until the end of study participation.

Participation of a patient in this clinical study may be discontinued for any of the following reasons:

- The patient withdraws consent or requests discontinuation from the study for any reason.
- Termination of the study by the Sponsor or the regulatory authority.
- If a patient develops COVID-19 and is unable to continue with study visits and observations, the patient should be discontinued from the study and standard of care CMV treatment should be initiated, if necessary. If COVID-19 treatment will be provided to the patient, the Investigator should notify the Medical Monitor prior to study discontinuation, if possible. All patients should be followed for safety and resolution of COVID-19 infection. Patients who are able to complete study-related visits as an outpatient or via home healthcare services (United States only) or are inpatient and can receive study treatment will be allowed to continue to participate in the study if they do not receive any experimental treatments for COVID-19.

In the case of patients lost to follow-up, attempts to contact the patient must be made and documented in the patient's medical records.

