6.4.3 Week 4 (Day 29)

The following procedures will be performed at Week 4 (Day 29):

- Record concomitant medications.
- Obtain body weight (prior to study drug administration).
- Perform complete physical examination (prior to study drug administration).
- Record vital signs (systolic and diastolic blood pressure, pulse rate, and body temperature) (prior to study drug administration).
- Collect blood samples for blood biochemistry, hematology, and coagulation for analysis by the local laboratory (Japan sites) and central laboratory (US sites) (prior to study drug administration).
- Collect urine sample for urinalysis by the local laboratory (Japan sites) and central laboratory (US sites) (prior to study drug administration) (if possible).
- Collect blood sample for CMV DNA analysis by the central laboratory (prior to study drug administration).

- Collect blood samples for CMV DNA analysis or CMV antigenemia testing for analysis by the local laboratory (prior to study drug administration).
- Collect blood sample for serum NPC-21 concentration measurement (within 2 hours prior to study drug administration and at 2 hours [\pm 30 minutes] following the beginning of the infusion).
- Collect blood sample for anti–NPC-21 antibody measurement (prior to study drug administration).
- Perform 12-lead ECG (prior to study drug administration).
- Administer NPC-21 (at a dose of 6 or 12 mg/kg of actual body weight [at Screening]) or placebo via an approximately 60-minute intravenous infusion at a constant rate of 5 mL/minute.

Note: Patients will be asked to remain at rest in the supine position, in principle, during study drug administration and should remain resting, in principle, from the end of study drug administration until the tests scheduled within 1 hour after study drug administration.

Note: If an adverse event occurs during study drug administration and the Investigator deems it necessary, deceleration, suspension, or resumption of study drug administration is allowed (see Section 5.5.3 for details).

- Record adverse events.

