9.4 Pregnancy Reporting

If a patient becomes pregnant during the study following administration of study drug or within 90 days following the last dose, the Investigator is to stop dosing with study drug immediately and the patient should be withdrawn from the study. Early termination procedures should be implemented at that time.

Pregnancy is not considered to be an adverse event or SAE; however, it must be reported to [REDACTED] within 24 hours of knowledge of the pregnancy.

[REDACTED] will then provide the Investigator/site the Exposure In Utero (EIU) form for completion. The Investigator/site must complete the EIU form and fax/email it back to [REDACTED].

If the female partner of a male patient becomes pregnant while the patient is receiving study drug or within 90 days following the last dose, the Investigator should notify [REDACTED] as described above and obtain informed consent for the collection of information regarding the pregnancy.

The pregnancy should be followed until the outcome of the pregnancy, whenever possible. Once the outcome of the pregnancy is known, the EIU form should be completed and faxed/mailed to [REDACTED]. If the outcome of the pregnancy meets the criteria for immediate

classification as an SAE (ie, postpartum complication, spontaneous abortion, stillbirth, neonatal death, or congenital anomaly), the Investigator should follow the procedures for reporting an SAE.

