- o. Perform within 1 hour of the end of the infusion.
- p. Vital signs will include systolic and diastolic blood pressure, pulse rate, and body temperature.
- q. Blood biochemistry includes liver function tests and enzymes. Hematology includes complete blood count with differential. Urine samples will be collected if possible. Blood biochemistry, hematology, coagulation, and urinalysis will be evaluated at the local laboratory at Screening and at the local laboratory (Japan sites) and central laboratory (US sites) prior to study drug administration on dosing days (Day 1 and at Weeks 4, 8, and 12) and at Weeks 1, 2, 6, 10, 14, 16, 20, 24, and 28. Samples for evaluation by the central laboratory may be collected by home healthcare services (United States only) at non-dosing day visits.
- r. A urine or serum pregnancy test will be performed at Screening and at Week 28 for all females of childbearing potential, and they must have a negative test result. An FSH test will be performed for females of non-childbearing potential (if necessary) at Screening. If a female patient of childbearing potential discontinues the study early, a urine or serum pregnancy test will be performed at the ET visit.
- s. Collect blood samples for CMV DNA analysis utilizing PCR analysis. The central laboratory will perform CMV PCR analysis. Samples for evaluation by the central laboratory may be collected by home healthcare services (United States only) at non-dosing day visits.

- t. Collect blood samples for CMV DNA or antigenemia testing. The local laboratory will perform CMV PCR analysis or CMV antigenemia testing consistently throughout the study.
- u. In the case home healthcare services (United States only) are utilized, it is not necessary to collect blood samples for CMV DNA analysis or CMV antigenemia testing for analysis by the local laboratory.
- v. Additional follow-up ECGs may be performed if clinically indicated.
- w. Administer NPC-21 (at a dose of 6 or 12 mg/kg of actual body weight [at Screening]) or placebo via an approximately 60-minute intravenous infusion at a constant rate of 5 mL/minute (Note: If an adverse event occurs during study drug administration and the Investigator deems it necessary, deceleration, suspension, or resumption of study drug administration is allowed).
- x. Collect blood sample for serum NPC-21 concentration measurements. Samples may be collected by home healthcare services (United States only) at non-dosing day visits.

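### Pregnancy is a reason to stop dosing at once, but no pregnancy test is scheduled from the first infusion (Day 1) to the last (Day 85)

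*Protocol*

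**What the plan says.** **The stop rule.** Protocol Section 4.3 opens its list with "Patients may be discontinued from study drug for any of the following reasons", and pregnancy is on the list. Section 9.4 is firmer. For a pregnancy after study drug has been given, or within 90 days of the last dose, "the Investigator is to stop dosing with study drug immediately and the patient should be withdrawn from the study".

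**The tests.** Inclusion criterion 6 (Synopsis and Section 4.1) says that women of childbearing potential "must have a negative urine or serum pregnancy test result at Screening". Appendix A, note r, gives the schedule: "A urine or serum pregnancy test will be performed at Screening and at Week 28 for all females of childbearing potential". For a woman who leaves the study early, the same note adds that "a urine or serum pregnancy test will be performed at the ET visit". The visit lists agree: a pregnancy test appears in Sections 6.2 (Screening), 6.5.6 (Week 28) and 6.7 (Early Termination). It does not appear in the dosing-day lists (6.4.1, 6.4.3, 6.4.5 and 6.4.7), at the other Treatment Period visits, or on entry to the Rescue Phase (6.6). Appendix B names the test but adds no time point, and the SAP adds none.

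**Prior exposure.** Section 1 states: "A first-in-human study was conducted in 40 healthy Japanese and Caucasian male volunteers". Section 1.1 describes it as a single-dose study and gives a half-life of 612.30 to 790.41 hours.

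**The concern.** The protocol treats pregnancy as serious enough to end dosing immediately, but it schedules no test that could bring a pregnancy to light while a dose is still to be given. A site that follows the schedule exactly could give several infusions after an unrecognised conception.

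What is at stake is repeated exposure to a long-lived antibody for which the documents describe no earlier use in women. The matter is one of patient safety and does not touch the trial's power or error rate.

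A second, smaller point concerns what follows a positive result. Section 4.3 says that patients who stop study drug for any reason stay in scheduled follow-up, while Section 9.4 withdraws a pregnant patient from the study. The difference reaches the primary endpoint: under Protocol Section 10.2.1 and SAP Section 3.4.1, a patient who leaves the study before Week 16 without a CMV event is in principle counted as a non-responder.

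**Working it through.** **Inputs**
- Infusions on Days 1, 29, 57 and 85 (Sections 6.4.1, 6.4.3, 6.4.5 and 6.4.7).
- Screening on Day -14 to Day -1 (Section 6.2); Week 28 is Day 197 (Section 6.5.6).
- There is no Day 0 (SAP Section 3.1.1), so Day d after dosing lies d - 1 days after Day 1, and Day -k lies k days before it.
- Visit window of ±3 days after Day 1 (Sections 6.4 and 6.5).
- 108 patients randomised 4:1:4 to 6 mg/kg, 12 mg/kg and placebo (Section 3.1).

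**1. Age of the Screening result at each infusion (nominal days)**

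| Infusion | Tested on Day -14 | Tested on Day -1 |
|---|---|---|
| Day 1 | 0 + 14 = 14 | 0 + 1 = 1 |
| Day 29 | 28 + 14 = 42 | 28 + 1 = 29 |
| Day 57 | 56 + 14 = 70 | 56 + 1 = 57 |
| Day 85 | 84 + 14 = 98 | 84 + 1 = 85 |

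**2. Last infusion to the Week 28 test.** 197 - 85 = 112 days, or 16 weeks, which matches Week 28 minus Week 12. Using both ±3-day windows the range is 106 to 118 days.

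**3. Can another scheduled test come in time?** No.
- The Early Termination test is done when the patient leaves the study, so no dose follows.
- Patients who complete rescue therapy have the Week 28 procedures at least 4 Study Weeks after their last dose (Section 6.6). That can be well before Day 197, but entry to the Rescue Phase is a listed reason to stop study drug (Section 4.3), so this test also follows the last dose.
- The Screening test precedes all dosing and acts through eligibility, not through the stop rule.

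The number of scheduled tests from Day 1 to Day 85 is therefore 0.

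**4. Persistence of the drug.** 612.30 / 24 = 25.5 days and 790.41 / 24 = 32.9 days, so the half-life is about 26-33 days, against a dosing interval of 28 days.

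**5. How many women.** The documents give no share of women of childbearing potential. I assume 10-25%, equal across arms.
- Patients on NPC-21: 108 × 5/9 = 60.
- Women of childbearing potential on NPC-21: 60 × 0.10 = 6 to 60 × 0.25 = 15.
- NPC-21 infusions in these women: at most 6 × 4 = 24 to 15 × 4 = 60. Some will receive fewer than four, since entering rescue ends dosing.

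**6. How many pregnancies.** Criterion 6 describes a highly effective method as one failing in under 1% per year with consistent and correct use. Taking one such method, the upper assumption of 27 women in all arms (108 × 0.25), and the 98 days from Day -14 to Day 85: 27 × 98/365 × 0.01 = 0.07. For the 15 women on NPC-21: 15 × 98/365 × 0.01 = 0.04. Imperfect use would raise these figures; the documents give no rate for it.

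**The case against.** The strongest reply is that nothing here conflicts. The Section 9.4 rule is triggered by pregnancy itself, however it becomes known, and not by a scheduled test. A reader might infer that rule and schedule contradict each other. They do not: the rule can operate under this schedule, and what is missing is a scheduled means of detection.

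A reader might also infer that detection rests wholly on the patient recognising her own pregnancy. The documents do not support that either. Every dosing visit includes a physical examination before the infusion, adverse event recording and a medication review; ineligibility found after randomisation is a reason to stop drug; and unscheduled tests are not forbidden.

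Contraception is the main mitigation. Criterion 6 requires two highly effective methods, or one plus condom and spermicide, throughout the study and for 90 days after the last dose. On those terms the expected number of pregnancies is well below one. This stands, and it limits how much weight the point can bear. It does not remove the gap, because the protocol keeps a stop rule for contraceptive failure and the rate of under 1% holds only with consistent and correct use.

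Two further inferences go too far. Infusions given to women of childbearing potential are not infusions given in pregnancy, and a count over all arms (about 43-108 on the same assumption) would include saline. Nor do the documents show fetal harm: the half-life shows persistence, and an all-male first study shows absence of data.

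**Conclusion.** The point holds as a gap between a safety rule and the schedule meant to serve it. Pregnancy tests are scheduled only at Screening, Week 28 and Early Termination. None falls from Day 1 to Day 85, and every test after Screening follows the patient's last dose. Until then the stop rule relies on patient report, clinical suspicion or unscheduled testing.

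The day counts follow directly from the protocol. The figure of 6-15 women on NPC-21, with at most 24-60 infusions, rests on the assumed 10-25% share and describes who could be affected, not how many will be. The expected number of pregnancies is small. The case for change rests on its low cost and on the absence of any described exposure in women; it does not rest on a contradiction in the rule or on demonstrated harm. The mismatch between Sections 4.3 and 9.4 on follow-up after pregnancy is separate and needs no assumption.

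**What to change.** - Reconcile the pregnancy-test schedule (Appendix A and its note r; Sections 6.4.1, 6.4.3, 6.4.5 and 6.4.7) with the stop rule in Sections 4.3 and 9.4, so that the schedule can support the rule while doses remain. The timing is for the sponsor to choose.
- Reconcile Section 4.3 with Section 9.4 on whether a patient who stops drug for pregnancy stays in scheduled follow-up or is withdrawn, so that her handling in the primary analysis is settled in advance.

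The cost is a small added test burden in women of childbearing potential only. Dosing visits are already in person, so no new visit is needed. It should not be assumed that samples already taken would give a result before the infusion: US safety blood goes to the central laboratory, and urine is collected only if possible. A test may therefore have to be run locally.

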NIMP	Non-investigational medicinal product (Note: Except for NPC-21 for this study)
PCR	Polymerase chain reaction
PK	Pharmacokinetic(s)
SAE	Serious adverse event
SAR	Serious adverse reaction
SOT	Solid organ transplant
SUSAR	Suspected Unexpected Serious Adverse Reaction
$t_{1/2}$	Half-life
VGCV	Valganciclovir
VZV	Varicella zoster virus
WHO	World Health Organization

1 INTRODUCTION AND BACKGROUND INFORMATION

Human cytomegalovirus (hCMV) is a member of the *Herpesviridae* family double-stranded deoxyribonucleic acid (DNA) viruses that become latent in host cells after acute infection. Cytomegalovirus (CMV) infection is ubiquitous and high seroprevalence has been reported in worldwide populations. In the United States, CMV seroprevalence ranges from 40% to 80%.^{1,2,3} Cytomegalovirus infection is usually harmless, except in the fetus and the immunocompromised host. In the immunocompromised host, primary infection, reinfection, or reactivation of latent virus can cause significant morbidity and mortality. Persons undergoing a solid organ transplant (SOT) are particularly susceptible to both primary infection and reactivation of CMV as a result of the pharmacologic immunosuppression used to prevent graft rejection.

Cytomegalovirus entry into host cells requires the stepwise coordination of multiple virus-encoded envelope proteins. Following viral attachment, which is mediated by interactions between the CMV glycoprotein M/glycoprotein N complex and host heparin sulfate proteoglycans,^{4,5} the virus envelope fuses with cellular membranes through the combination of glycoprotein B (gB) and glycoprotein H/glycoprotein L complexes. Glycoprotein B is essential for the attachment, entry, fusion, and cell-to-cell spread of CMV.⁵ In addition, gB is the dominant antigen on the CMV envelope, and close to 100% of CMV infected individuals develop antibodies against this glycoprotein.⁶ Antibody preadsorption experiments with recombinant-derived gB have shown that in some human sera, a considerable fraction of the neutralizing response is directed against gB.^{6,7}

Three antigenic sites, antigenic domain (AD)-1, AD-2, and AD-3, have been identified in gB and consist of amino acids (aa) 552 to 635, aa 50 to 77, and aa 783 to 906, respectively.^{8,9,10} Antigenic domain 1 is highly conserved among clinical CMV strains and is an essential structural domain for gB function.^{11,12,13} The majority of gB-specific antibodies that develop during natural CMV infection are directed against AD-1,¹⁴ and antibodies that bind to AD-1 can have virus-neutralizing capacity.^{15, 16} Therefore, AD-1 of CMV gB is a potential candidate region in targeting a neutralizing prophylactic and therapeutic antibody against CMV infection.

Human cytomegalovirus is usually transmitted as an inapparent infection during infancy and establishes a latent infection in T-lymphocytes, monocytes, macrophage cells, or salivary glands. When infected with hCMV for the first time during puberty or later, hCMV infection manifests as infectious mononucleosis-like symptoms, such as fever, swollen lymph nodes, and abnormal hepatic function. However, individuals with reduced immunity, such as those with acquired immunodeficiency, malignant tumors, SOT, and hematopoietic stem cell transplantation (HSCT), develop significant symptoms, such as pneumonia, retinitis, gastroenteritis, and encephalitis, resulting in a poor prognosis.

The morbidity and mortality associated with CMV infection are secondary to both the direct and the indirect effects of CMV. Cytomegalovirus infection can result in CMV disease, both CMV syndrome and CMV tissue-invasive disease. The highest risk of CMV disease occurs in CMV seronegative recipients of an organ from a CMV seropositive donor. Nearly 40,000 SOTs occur in the United States each year.¹⁷ The most common organ transplanted is the kidney, followed by the liver. Because of the immunosuppression required to prevent rejection of the graft, the host is predisposed to infections. Like HSCT recipients, CMV is one of the most important viral infections occurring in SOT. Not only is infection a risk factor for CMV disease, including CMV viral syndrome and tissue-invasive disease, it is also an independent risk factor for secondary bacteremia, Epstein-Barr virus-mediated, post-transplant lymphoproliferative disorder and

allograft injury.¹⁸ Peak viral load, rate of increase of viral load, and a threshold level of viremia have all been associated with risk for CMV disease.¹⁹ Highest risk persons for CMV infection and disease are those that are seronegative recipients paired with a seropositive organ donor. However, seropositive recipients are also at risk for disease.

In SOT recipients, hCMV is a causative virus for morbidity and mortality within 6 months of the transplant.^{20,21} In addition, hCMV has been reported to be involved in the risk of developing allograft injury or rejection^{22,23} and opportunistic infections.²⁴ In addition, it has been reported that in transplant recipients not receiving prophylaxis or preemptive treatment, the overall incidence of symptomatic CMV infections reached 40% to 60%, with the incidence and severity being highest among hCMV seronegative recipients transplanted from hCMV seropositive donors.²⁵ In HSCT recipients, CMV seropositive recipients are at the highest risk for the development of CMV infection regardless of the donor's CMV serostatus. Without intervention, approximately 80% of CMV seropositive HSCT patients will experience CMV infection (viremia) and approximately 30% of patients with CMV viremia will develop CMV disease.²⁶

Human cytomegalovirus infection causes organ damage (direct effect) after the stage of hCMV viremia, and affects chronic inflammation and the immune system, leading to acute rejection and the development of new infections (indirect effect). Prevention of hCMV infection is thus critically important for successful organ transplantation. The mainstay in clinical practice is prophylaxis or preemptive treatment with antiviral drugs given transplantation in SOT and HSCT recipients. The first-line antiviral drug used in the treatment is ganciclovir (GCV) or valganciclovir (VGCV). However, the use of GCV, VGCV, and other antiviral drugs raises concerns about serious adverse drug reactions (ADRs), such as bone marrow depression and renal disorder as well as the development of GCV-resistant strains.²⁷ As an alternative approach, CMV antibodies have been used successfully to treat CMV-induced disease. For example, CMV hyperimmunoglobulin has demonstrated efficacy in certain SOT recipients,²⁸ and a more recent study found that pooled human immunoglobulin G products from CMV-positive individuals are effective in protecting infants from congenital CMV infection.²⁹ Likewise, letermovir, a CMV agent intended for prophylaxis, became available recently for use in allogeneic HSCT patients, but its potential risks of drug interaction with immunosuppressive agents and antiviral resistance may limit treatment options.³⁰ Therefore, the development of a novel drug that provides an effective and safe alternative or addition to current CMV therapies is necessary.

NPC-21 is a human monoclonal immunoglobulin G1 (IgG1) lambda against the AD-1 on hCMV gB. Antigenic domain 1, the dominant antigen of the hCMV envelope, is reported to exhibit little sequence variation in clinical isolates of hCMV.¹³ A cell clone that produces NPC-21 was selected from B-lymphocytes isolated from peripheral blood of a healthy individual with a history of CMV infection. NPC-21 is produced by recombinant DNA technology in Chinese hamster ovary cells. NPC-21 has been demonstrated *in vitro* to inhibit infection of a cultivated CMV strain in the pharmacology study using ARPE-19 cell (epidermal cell line).

NPC-21 is a non-immunomodulatory human monoclonal antibody with a relatively safe toxicological profile, causing no deaths and producing only mild reversible changes in hematological parameters (ie, decreased erythrocyte count, hematocrit value, and hemoglobin concentration) following repeated dosing in monkeys. Additionally, no cross reactivity was seen in a study of cross reactivity in human and monkey tissue. Although these changes occurred at a dose with sufficient safety margins and after repeated doses, the hematology parameters will be carefully monitored in clinical studies.

A first-in-human study was conducted in 40 healthy Japanese and Caucasian male volunteers in which NPC-21 or placebo was infused over a duration of 60 minutes. This single ascending dose study confirmed tolerability of NPC-21 up to 20 mg/kg, with no serious adverse events (SAEs), ADRs, or withdrawals due to adverse events. Anti-NPC-21 antibodies were detected in some subjects, although all were found to be preexisting conditions.

Taken together, nonclinical data and clinical data available to date support further clinical investigation of NPC-21 in the prevention of CMV disease.

In March 2020, the Coronavirus Disease 2019 (COVID-19), caused by infection with severe acute respiratory syndrome coronavirus 2, was characterized as a pandemic by the World Health Organization (WHO). The COVID-19 pandemic impacted clinical studies worldwide due to quarantines, site closures, travel limitations, diversion of resources, and/or general interruptions in study-related procedures.

This study protocol includes contingency measures to manage disruptions due to COVID-19; see Section 5.6.2 for information regarding acceptable COVID-19 vaccines and medications and Sections 6, 7.3, 7.4, 8.1, 8.2, 9.7, 9.8, 9.9, 9.10, and 9.12 and Appendix A for details on procedures that may be performed by home healthcare services (United States only) due to COVID-19 restrictions or other concerns, such as the need to avoid risks of COVID-19 infection. The impacts of these implemented contingency measures on the outcomes of this study, including any protocol deviations that result from COVID-19 illness and/or COVID-19 control measures will be discussed in the Clinical Study Report.

